TITLE:	LONG-TERM NON-INTERVENTIONAL	
	SAFETY STUDY OF EMICIZUMAB TREATMENT IN	
	PATIENTS WITH MODERATE HAEMOPHILIA A	
	AND SEVERE BLEEDING PHENOTYPE	
	(STUDY BO44691, PASS)	
PROTOCOL NUMBER:	BO44691	
VERSION NUMBER:	V2.0	
EU PAS REGISTER NUMBER:	To be determined	
STUDIED MEDICINAL PRODUCT:	Emicizumab (RO5534262, ACE910, HEMLIBRA®)	
AUTHOR:	PhD,	
	F. Hoffmann - La Roche Ltd, Basel, Switzerland	
	Phone:	
DATE FINAL:	See electronic date stamp below	

NI PASS PROTOCOL (SECONDARY DATA USE)

|CONFIDENTIAL

This non-interventional study is managed by F. Hoffmann-La Roche Ltd of Basel, Switzerland. However, it may be implemented in individual countries by Roche's local affiliates, including Genentech, Inc. in the United States. The information contained in this document, especially any unpublished data, is the property of F. Hoffmann-La Roche Ltd (or under its control) and therefore is provided to you in confidence. It is understood that this information will not be disclosed to others without written authorization from Roche except to the extent necessary.

Hemlibra—F. Hoffmann-La Roche Ltd

Protocol BO44691, Version 2.0

PRODUCT REFERENCE NUMBER: EMEA/H/C/004406 PROCEDURE NUMBER{S}: NA JOINT PASS No RESEARCH QUESTION AND OBJECTIVES: The study aims to evaluate the long-term safety profile (with focus on thromboembolic [TE] events) of emicizumab in patients with moderate congenital Haemophilia A (1% ≤ Factor VIII [FVIII] ≤ 5%), withou FVIII inhibitors and with severe bleeding phenotype, who are exposed to emicizumab in real-world settings. The primary objective for this study is to determine the incidence of TE events. The secondary objectives for this study are: 1. To determine the incidence of serious adverse events (SAEs). 2. To determine the incidence of thrombotic microangiopathy (TMA) events. 3. To determine the incidence of serious systemic hypersensitivity reactions, including anaphylaxis. 4. To characterise the risk profile in terms of
PROCEDURE NUMBER{S}: NA JOINT PASS No RESEARCH QUESTION AND OBJECTIVES: The study aims to evaluate the long-term safety profile (with focus on thromboembolic [TE] events) of emicizumab in patients with moderate congenital Haemophilia A (1% ≤ Factor VIII [FVIII] ≤ 5%), withou FVIII inhibitors and with severe bleeding phenotype, who are exposed to emicizumab in real-world settings. The primary objective for this study is to determine the incidence of TE events. The secondary objectives for this study are: 1. To determine the incidence of serious adverse events (SAEs). 2. To determine the incidence of serious systemic hypersensitivity reactions, including anaphylaxis. 4. To characterise the risk profile in terms of
JOINT PASS No RESEARCH QUESTION AND OBJECTIVES: The study aims to evaluate the long-term safety profile (with focus on thromboembolic [TE] events) of emicizumab in patients with moderate congenital Haemophilia A (1% ≤ Factor VIII [FVIII] ≤ 5%), withou FVIII inhibitors and with severe bleeding phenotype, who are exposed to emicizumab in real-world settings. The primary objective for this study is to determine the incidence of TE events. The secondary objectives for this study are: 1. To determine the incidence of serious adverse events (SAEs). 2. To determine the incidence of serious systemic hypersensitivity reactions, including anaphylaxis. 4. To characterise the risk profile in terms of
RESEARCH QUESTION AND OBJECTIVES: The study aims to evaluate the long-term safety profile (with focus on thromboembolic [TE] events) of emicizumab in patients with moderate congenital Haemophilia A (1% ≤ Factor VIII [FVIII] ≤ 5%), withou FVIII inhibitors and with severe bleeding phenotype, who are exposed to emicizumab in real-world settings. The primary objective for this study is to determine the incidence of TE events. The secondary objectives for this study are: 1. To determine the incidence of serious adverse events (SAEs). 2. To determine the incidence of thrombotic microangiopathy (TMA) events. 3. To determine the incidence of serious systemic hypersensitivity reactions, including anaphylaxis. 4. To characterise the risk profile in terms of

3. ABSTRACT/SYNOPSIS

TITLE:	LONG-TERM NON-INTERVENTIONAL SAFETY STUDY OF EMICIZUMAB TREATMENT IN PATIENTS WITH MODERATE HAEMOPHILIA A AND SEVERE BLEEDING PHENOTYPE (STUDY BO44691, PASS)	
PROTOCOL NUMBER:	BO44691	
VERSION NUMBER:	2.0	
DATE OF SYNOPSIS:	November 2023	
EU PAS REGISTER NUMBER:	To be determined	
STUDIED MEDICINAL PRODUCT:	Emicizumab (RO5534262, ACE910, HEMLIBRA®)	
SCIENTIFIC RESPONSIBLE:		
MAIN AUTHOR:		
PHASE:	IV, non-interventional study	
INDICATION:	Moderate congenital Haemophilia A ($1\% \le FVIII \le 5\%$), without FVIII inhibitors and with severe bleeding phenotype	
MARKETING AUTHORISATION HOLDER:	Roche Registration GmbH [name]	

Rationale and Background

Haemophilia A (HA) is a congenital form of haemophilia causing a lack of coagulation factor VIII (FVIII). Bleeding often occurs in joints and can result in severely damaged and deformed joints; it can also occur in any other part of the body and can be life-threatening.

The goal of haemophilia treatment is to reduce the risk of bleeding and other complications of the disorder. Haemophilia treatment of more severe cases have traditionally relied on FVIII infusions that often poses a significant burden on the patient and even during prophylactic treatment patients can experience a high rate of bleeding events.

Hemlibra—F. Hoffmann-La Roche Ltd Protocol BO44691, Version 2.0

Emicizumab (Hemlibra®) is a recombinant, humanised, bispecific monoclonal antibody that mimics the function of activated FVIII without being structurally similar, meaning that emicizumab is not linked to the development or is affected by the presence of FVIII inhibitors. The use of subcutaneous (SC) injection as the route of administration also results in significantly lower patient burden of treatment.

In the European Union (EU), the marketing authorisation holder (MAH) submitted an extension of indication for Hemlibra to include routine prophylaxis of bleeding episodes in patients with congenital HA without FVIII inhibitors who have moderate disease ($1\% \leq$ FVIII \leq 5%) with severe bleeding phenotype.

On 15 December 2022, the committee for medicinal products for human use (CHMP) issued a positive opinion for this new extension of indication; European commission (EC) decision was received on 23 January 2023.

To fulfil the resultant category 3 post-authorisation safety study (PASS) regulatory commitment in the EU, the MAH proposed a multi-registry PASS study to characterise the important potential risk of thromboembolic (TE) events (not associated with activated prothrombin complex concentrates [aPCC] exposure) specifically and inform on the long-term safety profile of emicizumab in the new patient population.

Research Question and Objectives

The aim of the study is to evaluate the long-term safety profile of emicizumab in patients with moderate congenital HA ($1\% \le FVIII \le 5\%$) without FVIII inhibitors and with severe bleeding phenotype and who are exposed to emicizumab in real-world settings, with a specific focus on TE events.

The primary objective for this study is to determine the incidence of TE events.

The secondary objectives for this study are:

- 1. To determine the incidence of serious adverse events (SAEs).
- 2. To determine the incidence of thrombotic microangiopathy (TMA) events.
- 3. To determine the incidence of serious systemic hypersensitivity reactions, including anaphylaxis.
- 4. To characterise the risk profile in terms of pre-defined risk factors of TE events in the patient population.

Hemlibra—F. Hoffmann-La Roche Ltd Protocol BO44691, Version 2.0

- 5. To describe characteristics of TE events, SAEs, TMA events, and serious systemic hypersensitivity reactions, including anaphylaxis (e.g., diagnosis and symptoms).
- 6. To characterise the impact of the prior use of FVIII prophylaxis on the incidence of TE events, SAEs, TMA events, and serious systemic hypersensitivity reactions, including anaphylaxis.

Study Design

This non-interventional (NI) PASS is a multi-country, registry-based, longitudinal cohort study based on secondary use of data collected for patients of all ages with moderate congenital HA, without FVIII inhibitors and with severe bleeding phenotype, treated with emicizumab

Patients will be assessed for inclusion during the cohort entry period, this will last from market authorisation of emicizumab for use among moderate patients without inhibitors in each participating country until approximately Q4 2026.

Patients will be followed from the index date, which will be the date of emicizumab treatment initiation for each patient during the cohort entry period, until discontinuation of emicizumab, death, end of observation (due to loss to follow-up, emigration, or disenrollment from the registry), a maximum of 5 years, or end of study period (anticipated Q4 2030), whichever occurs first.

Data Sources

This PASS will use data routinely collected within registries containing haemophilia patients primarily but not limited to the European region. The specific registries considered for this study were determined in a feasibility study that was conducted to identify the most appropriate data sources for this study. Participation of each data source is conditional to contracting. The considered data sources are listed below:

- UK National haemophilia database (United Kingdom)
- FranceCoag registry / Reseau FranceCoag (France)
- HemoNED (Netherlands)
- American Thrombosis and Hemostasis Network dataset (United States)
- World Bleeding Disorders Registry (Multi-country)
- Canadian Bleeding Disorders Registry (Canada)

Population

Inclusion criteria:

- Diagnosis of congenital HA;
- Moderate disease classification (1% ≤ FVIII ≤ 5%);
- Severe bleeding phenotype;

Hemlibra—F. Hoffmann-La Roche Ltd

Protocol BO44691, Version 2.0

The above-mentioned inclusion criteria will ensure that the patient is eligible for the extended indication of emicizumab.

In addition, the patient will have to fulfil the following criteria:

- Initiation of emicizumab treatment during the cohort entry period;
- Information on previous HA outcomes and HA treatments approximately 12 months prior to the index date. In case HA diagnosis occurred within 12 months of the index date, the required lookback period will be shortened to time from HA diagnosis to index date. Anamnestic information capturing historic events but entered in the registry database less than 12 months before the index date will be considered as long as they were recorded prior to the index date;
- Information on risk factors of TE events (e.g., medical comorbidities, treatments and demographic characteristics) approximately 12 months prior to the index date. If the patient is below 1 year of age, the lookback period will be shortened to birth until index date. Anamnestic information capturing historic events but entered in the registry database less than 12 months before the index date will be considered as long as they were recorded prior to the index date;
- Signed the informed consent form where required by local regulations.

Exclusion criteria:

- Development of FVIII inhibitors any time before the index date;
- Treatment with emicizumab at any time before the index date.

Variables

Primary Safety Variables

The primary variables for this study are as follows:

TE events

Secondary Variables

The secondary variables for this study are as follows:

- SAEs
- TMA events
- Serious systemic hypersensitivity reactions, including anaphylaxis
- Demographic characteristics
- Time since diagnosis of congenital HA
- Prior treatments for haemophilia
- HA medical history
- Concomitant medications
- Other medical history and concurrent conditions
- Risk factors for TE events.

Study Size

Projected real-world study size based on feasibility study and existing literature on prevalence of inhibitors and moderate HA population, indicates ~202 patients newly

exposed to emicizumab can be captured with a total study population of 3000 moderate HA patients, within the cohort entry period.

Study size estimations were done via simulations to assess whether the real-world estimate is adequate for the primary objective of estimating the crude incidence rate (IR) of 1st TE events by varying sample size targets, expected event rates and threshold value for 95% Clopper-Pearson confidence interval (CI). Simulations were run to calculate expected accuracy defined as the probability that the CI of the crude IR does not exceed an upper threshold.

Approximately 200 emicizumab exposed patients across all study countries will be necessary with an average follow-up of 4 years for each patient, to achieve 88% probability that the 95% Clopper-Pearson CI of the crude IR does not exceed a threshold value of one event per 100 person-years (PY). This assumes an expected crude IR of TE events of 0.15 events per 100 PY.

Data Analysis

This study does not include any formal comparison and is purely descriptive. A common data model (CDM) will be used to create aggregated data, either by the data source or by IQVIA. This CDM will define the level of aggregation and minimum information required to enable the statistical analysis of the study objectives. The aggregated datasets will be pooled for the statistical analysis.

For the primary objective, crude IRs for 1st TE events during the follow-up period per 100 PY will be described. For the calculation of crude IRs, the denominator will be the pooled person-time of all the patients within the cohort and the numerator will be all first events occurring during the follow-up period. In addition of crude IRs, incidence proportions will also be calculated.

For the analysis of secondary objectives 1, 2, 3, 4 and 6, crude IRs per 100 PY will be calculated and for secondary objective 5, descriptive tabulations will be done for SAE and TE events.

For secondary objective 1, 2, 3 the numerators will be the number of first occurrences of any SAE, 1st TMA events and 1st serious systemic hypersensitivity reaction events during the follow-up period, respectively. The denominators for the crude IRs will be the pooled person-time. For secondary objective 4, the events will be counted for each category/stratum of relevant pre-defined risk factors of TE events, to yield crude IRs of TE per category/stratum. For analysis of secondary objective 5, characteristics of TE events, SAEs, TMA events, and serious systemic hypersensitivity reactions, including anaphylaxis (e.g., diagnosis and symptoms), will be tabulated. In addition, time to the 1st

TE events, SAE, TMA events, and serious systemic hypersensitivity reactions, including anaphylaxis events will be described by Kaplan-Meier curves. For analysis of secondary objective 6, calculation of crude IR and crude incidence proportion of TE events, SAEs, TMA events, and serious systemic hypersensitivity reactions, including anaphylaxis, will be calculated, and tabulated for FVIII prophylaxis use (yes/no) prior to emicizumab treatment.

All crude IRs will be presented with 95% CI. For continuous variables, the number of observations, mean, standard deviation, median, lower (1st) and upper (3rd) quartiles, interquartile range (IQR), minimum, maximum, as well as 5th and 95th percentiles will be presented. For categorical variables, the numbers, and percentages of observations for each of the categories will be presented. Numbers and percentages of missing values will be presented.

Milestones

First Data Extraction:

The first data extraction is the date from which the variables used for the analysis as per protocol start to be extracted. The planned first data extraction is approximately 1 year after study launch. The planned first data extraction is Q2 2025.

Last Data Extraction:

The last data extraction is the date after the last included patient has completed their minimum follow-up of 4 years. The planned last data extraction date is Q4 2030.

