The development of inhibitory alloantibodies (inhibitors) occurs in approximately 20%–30% of patients with severe congenital HA and in 3%–13% of those with moderate or mild disease (Franchini and Mannucci, 2013). The only haemostatic options previously available were pro-thrombotic coagulation factors that augment other parts of the coagulation cascade (i.e., "bypassing agents") (Srivastava et al., 2020).

Hemlibra (also known as emicizumab, ACE910, and RO5534262) is a recombinant, humanised, bispecific, immunoglobulin G4 monoclonal antibody (IgG4) that binds with moderate affinity to activated factor IX (FIXa) and factor X (FX). In patients with congenital HA, Hemlibra bridges FIXa and FX to restore the function of missing activated FVIII that is needed for effective haemostasis. In patients with congenital HA, haemostasis can be restored irrespective of the presence of FVIII inhibitors, as Hemlibra shares no sequence homology with FVIII. In addition, Hemlibra offers the subcutaneous (SC) administration, removing the need for venous access. The recommended dose for emicizumab is 3 mg/kg of bodyweight weekly during the first 4 weeks. Maintenance dosage from week 5 and onwards is either 1.5 mg/kg weekly, 3 mg/kg every 2 weeks, or 6 mg/kg of bodyweight every 4 weeks. Because of the possibility of markedly extended dosing intervals, to once weekly or even less frequently, this compound dramatically change the treatment of patients with congenital HA with and without FVIII inhibitors who need effective, safe, and convenient prophylactic therapy.

Hemlibra received a marketing authorisation (MA) valid throughout the EU on 23 February of 2018 for the indication: routine prophylaxis of bleeding episodes in patients with congenital HA with FVIII inhibitors. On 31 January of 2019, the EU committee for medicinal products for human use (CHMP) adopted a favourable opinion on the expansion of the indication of Hemlibra to patients with severe congenital HA without FVIII inhibitors. Hemlibra can be used in all age groups.

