8.2.5. Censoring

Patients will be followed until the end of study period or when meeting any of the following censoring criteria, the reason for censoring will be described, whichever occurs first:

- Death
- End of observation, e.g., due to loss to follow-up, emigration, or disenrollment from the registry
- Discontinuation of emicizumab treatment (as defined in the exposure section 8.3.2.2.)

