8.2.6.2. Exclusion Criteria

Patients will be excluded from the study if they meet any of the following criteria:

- Noted development of FVIII inhibitors in the data source any time before index date or fulfilling any of the following criteria of a previously developed algorithm (Batt et al., 2022):
 - Treatment with bypassing agents, such as aPCC or recombinant activated FVII (rFVIIa), at any time prior to the index date.
 - Treatment with rituximab at any time prior to the index date, this criterion would not apply if it was noted in the data source that it was used for another indication, e.g., treatment of lymphoma.
 - Noted use of assay to measure FVIII inhibitors (Duncan et al., 2013) and high dose of FVIII use at any time prior to the index date that is in line with immune tolerance induction. The exact definition of dosage in line with immune tolerance induction will be further defined in the statistical analysis plan (SAP) and may be data source specific.
- Treated with emicizumab at any time prior to the index date.

These criteria will ensure that the patient is eligible for the extended indication of emicizumab.

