8.7.2. Planned Analyses

For the analysis of the primary objective and secondary objectives 1, 2, and 3 the overall crude and crude stratified IRs will be calculated. The person-time of each patient will be based on the follow-up and censoring criteria presented in section 8.2.4. and 8.2.5.

For the calculation of crude IRs, the denominator will be the pooled person-time of all the patients within the cohort. The patient time-at-risk will be calculated from index date until the date of an incident event or censoring, whichever occurs first. All first events occurring during follow-up period will be counted in the total number of events. Crude IRs will be presented per 100 PY with 95% CI.

For the primary objective, the numerator will be the number of first TE events of all patients within the cohort. For secondary objectives 1, 2, 3 the numerator will be the number of first occurrences of any SAE; TMA events or serious systemic hypersensitivity reactions, including anaphylaxis; respectively.

For the analysis of secondary objective 4, calculation of crude stratified IRs of 1st TE events will be done. The events will be counted for each category/stratum of relevant pre-defined risk factors (see section 8.3.2.4. for a listing of considered risk factors). More details on the risk factor based tabulations will be presented in SAP.

For analysis of secondary objective 5, characteristics of TE events, SAEs, TMA, and serious systemic hypersensitivity reactions, including anaphylaxis (e.g., diagnosis and symptoms), will be tabulated. In addition, time to 1st TE event; time to 1st TMA event; time to 1st serious systemic hypersensitivity reactions, including anaphylaxis; and time to any 1st SAE event will be described by Kaplan-Meier curves.

For analysis of secondary objective 6, calculation of crude IR and crude incidence proportion of TE, TMA events, SAEs and serious systemic hypersensitivity reactions, **Hemlibra—F. Hoffmann-La Roche Ltd** Protocol BO44691, Version 2.0

including anaphylaxis, will be calculated and tabulated for FVIII prophylaxis use (yes/no) prior to emicizumab treatment.

Patient demographic and clinical characteristics will also be tabulated in relation to the AEs (TE events, SAEs, TMA events and serious systemic hypersensitivity reactions, including anaphylaxis) and in total.

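### Freedom from FVIII inhibitors and bypassing agents is required only before index, and no planned rate separates events and person-time after a later inhibitor or aPCC/rFVIIa use

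*Protocol*

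**What the plan says.** Sections 3 and 7.1 limit the research question to patients without FVIII inhibitors. Sections 3 and 6.2 give the regulatory purpose as characterising TE risk that is unrelated to aPCC exposure.

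Both conditions are applied at entry only. The synopsis excludes "Development of FVIII inhibitors any time before the index date". Section 8.2.6.2 excludes "Noted development of FVIII inhibitors in the data source any time before index date" and adds markers of an inhibitor, among them "Treatment with bypassing agents, such as aPCC or recombinant activated FVII (rFVIIa), at any time prior to the index date".

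Follow-up in the synopsis runs "until discontinuation of emicizumab, death, end of observation (due to loss to follow-up, emigration, or disenrollment from the registry), a maximum of 5 years" or the end of the study. Section 8.2.5 lists death, end of observation and stopping emicizumab. In Section 8.7.2, "The patient time-at-risk will be calculated from index date until the date of an incident event or censoring, whichever occurs first", and "the denominator will be the pooled person-time of all the patients within the cohort". Section 8.3.1 counts TE events as the data source records them, without reference to aPCC.

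Table 2 lists FVIII inhibitor status only under the entry criteria. The subgroups in Section 8.7.3 are assessed at index. Of the four sensitivity analyses in Table 10, three extend follow-up or count repeat events and the fourth varies the bleeding-phenotype definition.

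**The concern.** A patient who develops an inhibitor, or receives aPCC or rFVIIa, after index no longer matches the stated target but keeps contributing to the rates for the primary objective and secondary objectives 1-3. The protocol has its own reasons for care here. Section 6.1 describes bypassing agents as "pro-thrombotic coagulation factors that augment other parts of the coagulation cascade". The planning rate in Section 8.5.2, 0.15 per 100 person-years (PY), is for serious TE events without concomitant aPCC. After index, the primary rate is thus wider than both the stated purpose and the figure it will be read against.

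The expected event count is so small that one event can set the result. No planned rate would let a reader see what remains when such an event and its person-time are removed.

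**Working it through.** **Inputs.** From Section 8.5.2: about 200 patients, average follow-up 4 years, expected rate 0.15 per 100 PY, threshold 1 per 100 PY, stated probability 88%. Section 6.1 gives inhibitors in 3-13% of moderate or mild disease, without a time frame. The protocol gives no incidence of inhibitors or of bypassing-agent use after index.

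**1. The plan's own figure.** Person-time is 200 × 4 = 800 PY and expected events are 800 × 0.0015 = 1.2. With person-years treated as binomial trials, the upper 95% Clopper-Pearson limit for x events is the 0.975 quantile of Beta(x + 1, 800 − x):

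| Events | Rate per 100 PY | Upper limit per 100 PY |
|---|---|---|
| 0 | 0 | 0.46 |
| 1 | 0.125 | 0.69 |
| 2 | 0.25 | 0.90 |
| 3 | 0.375 | 1.09 |

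At most 2 events meet the threshold, and P(X ≤ 2) = 0.880. This reproduces the 88%; the other five cells of Table 9 also reproduce. The sample-size calculation is not in question.

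**2. Weight of a single event.** One event after an inhibitor or on a bypassing agent, added to one other event, moves the rate from 0.125 to 0.25 and the upper limit from 0.69 to 0.90. Added to two others, it moves the upper limit from 0.90 to 1.09, past the threshold. Any additional event would do the same. The difference is that this one would lie outside the stated target.

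**3. How much time could be affected.** Assume that 1-3% of patients develop an inhibitor during follow-up and contribute 2-3 years afterwards.
- Patients: 200 × 0.01 = 2 to 200 × 0.03 = 6.
- Person-time: 2 × 2 = 4 PY to 6 × 3 = 18 PY, which is 0.5% to 2.25% of 800.
- Expected TE events in that time at the planning rate: 4 × 0.0015 = 0.006 to 18 × 0.0015 = 0.027. At ten times that rate: 0.06 to 0.27.

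Bypassing-agent use without a recorded inhibitor would add to this, and the protocol gives no figure for it.

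**4. Effect on the planned precision if the time is kept.** With share f of person-time at m times the planning rate, the pooled rate is 0.15 × [(1 − f) + f·m] per 100 PY. The probability is P(X ≤ 2) at 800 PY:

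| f | m | Pooled rate per 100 PY | Probability |
|---|---|---|---|
| 0.5% | 3 | 0.152 | 88% |
| 0.5% | 10 | 0.157 | 87% |
| 2.25% | 3 | 0.157 | 87% |
| 2.25% | 10 | 0.180 | 82% |

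**5. Cost of the split.** Removing 4-18 PY leaves 796-782 PY. Two events still meet the threshold, and at 0.15 per 100 PY the probability is 88-89%. Two events stop meeting it only below 720 PY, a loss of more than 10%. At 696 PY the probability is 72%.

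**The case against.** The strongest reply is that this is a new-user cohort with eligibility fixed at index. Section 8.2.6.2 says the exclusions serve to establish eligibility for the extended indication, and the aim is real-world safety. Later time on emicizumab is part of the treatment course. Keeping it hides no events, while cutting follow-up at a clinical event may introduce informative censoring, which Section 8.9.2 already raises for treatment stopping. This stands. It is why the primary rate should remain undivided.

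A reader might infer that an inhibitor on emicizumab brings bypassing agents into use. The documents do not say so. The sentence in Section 6.1 concerns the options formerly available, and the same section says emicizumab works irrespective of inhibitors.

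A reader might also infer that a bypassing-related event would be invisible. That goes too far. Section 8.3.2.1 foresees event-level detail on additional haemophilia treatments where available, and Section 8.3.2.2 says all registers cover aPCC and eptacog alfa. But this detail describes the event. It removes neither the event nor the person-time from any rate.

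A split at the inhibitor date alone would not isolate aPCC-related events. This is also right, so the cut has to include bypassing-agent use.

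Finally, recording may be uneven. Table 6 labels inhibitors as captured in all six registries, which its key defines as completeness not disclosed. The WBDR adverse-event categories in Section 8.3.1 do not name inhibitors, although Section 8.4 places inhibitor status in its minimal dataset. This is a limitation to state, not a reason to omit the analysis.

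The SAP could hold the analysis, but follow-up, censoring and time at risk are fixed in this protocol.

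**Conclusion.** The point holds as a gap between the stated target and the planned rates. It is not an error in the primary analysis. The documents do not support reading it as a contradiction that invalidates the primary rate or requires censoring at inhibitor onset.

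The expected effect is small. Under the assumed 1-3% incidence, 0.5-2.25% of person-time is affected, and the 88% probability falls to 82% only at the upper end of that range with a tenfold TE rate. Both the incidence and the rate multiple are assumptions, and the true share may be zero. What makes the point worth acting on is the 1.2 expected events: one event outside the target would materially change the rate, and no planned analysis gives the rate without it.

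Timing matters. WBDR and CBDR give no patient-level access (Table 7) and hold 2987 + 299 = 3286 of 5307 moderate patients, or 62%. Under Section 8.6 they aggregate their own data to a specification supplied to them. If that specification omits the dates, the split may not be recoverable from the delivered aggregates.

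**What to change.** Keep the undivided crude rate as primary. Add a fifth sensitivity analysis to Section 8.7.4 and Table 10, for the primary objective and secondary objectives 1-3. It should count events and person-time only up to the first recorded FVIII inhibitor or the first aPCC/rFVIIa use after index, whichever comes first. Report separately the number of patients who reach that point, their later person-time and their later events.

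Add the date of the first post-index inhibitor and the post-index bypassing-agent dates to Table 2 and to the common data model specification before the first extraction, planned for Q2 2025.

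The cost is two follow-up variables and one further set of aggregates per registry. The limitations to state are a small loss of person-time in that analysis, possible informative censoring at the cut, and uneven inhibitor recording across registries. The sample size and the primary analysis do not change.
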